#### **5.6.1.3. Missing Start and Stop Dates for Concomitant Medications**

Missing start dates for concomitant medications are not imputed.

Concomitant medications with incomplete end dates are considered concomitant medications if:

- Day and month are missing, and the year is equal to or after the year of the first date of study drug administration.
- Day is missing and the year is after the year of the first date of study drug administration.
- Day is missing and the year is equal to the year of the first date of study drug administration and the month is equal to or after the month of the first date of study drug administration; or
- Year is missing.

### **5.6.2. Missing Start and Stop Dates for Adverse Events**

Treatment-emergent adverse events (TEAEs) are defined in Section 9.1.

Adverse events with incomplete start dates are considered after the date of first dose, and therefore treatment emergent, if:

- Day and month are missing, and the year is equal to or after the year of the first date of study drug dosing;
- Day is missing and the year is after the year of the first date of study drug dosing;
- Day is missing and the year is equal to the year of the first date of study drug dosing and the month is equal to or after the month of the first date of study drug dosing; or
- Year is missing.

Adverse events with incomplete start dates or end dates are considered on or within 30 days of last dose, if:

- Day, month, and year are missing.
- Day and month are missing, and the year is equal to or before the year of the date of last dose of study drug plus 30 days;
- Day is missing and the year is equal to or before the year of the date of last dose of study drug plus 30 days and month is equal to or before the month of the date of last dose of study drug plus 30 days;

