## **11.6. Recording Adverse Events**

All conditions present prior to the administration of the first dose of study drug (Day 1) should be documented as medical history. After the first dose, documentation of AEs shall continue until the last study follow-up visit, regardless of the relationship of the AE to study drug.

Information to be collected includes type of event, date of onset, date of resolution, investigator-specified assessment of severity and relationship to study drug, seriousness, as well as any action taken.

While an AE is ongoing, changes in the severity (e.g., worsening and improving) should be noted in the source documents, but when documenting the AE, only the total duration and greatest severity should be recorded in the eCRF. AEs characterized as intermittent require documentation of onset and duration.

All drug-related (possibly, probably, or definitely related, see Section 11.4) AEs and abnormal laboratory test results reported or observed during the study must be followed to resolution (either return to baseline or within normal limits). All other AEs will be followed through the final visit indicated in [Table 4](#), as appropriate.

AEs resulting from concurrent illnesses, reactions to concurrent illnesses, reactions to concurrent medications, or progression of disease states must also be reported. Preexisting conditions (present before the start of the AE collection period) are considered concurrent medical conditions and should NOT be recorded as AEs. However, if the patient experiences a worsening or complication of such a concurrent condition, the worsening or complication should be recorded as an AE. Investigators should ensure that the AE term recorded captures the change in the condition (e.g., "worsening of..."). Any improvement in condition should be documented per Section [9.10.11](#).

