### 9.1. Adverse Event Preferred Term and Body/Organ System Summary Tables

Treatment-emergent adverse events (TEAEs) are summarized by treatment as defined by the safety analysis set.

Treatment-emergent adverse events (TEAEs) are events that either:

- Have a date of onset on or after the date of first dose and not more than 30 days after the date of the last dose of study drug, or
- Have no recorded date of onset with a stop date after the first dose of study drug, or
- Have no recorded date of onset or stop date.

General considerations for TEAE summaries are:

- Multiple events by preferred term (PT) and system organ class (SOC) are counted once only per patient for summaries of TEAE incidence.
- For summaries of TEAE incidence by severity, only the most severe event is counted per patient.
- For summaries of TEAE incidence by relationship, only the most related event is counted per patient.
- A TEAE with a missing resolution date or incomplete date that is not identified as continuing is assumed to be continuing.
- For summaries of the number of TEAE events, all TEAEs are counted.
- Withdrawal TEAEs include the subset of TEAEs that started one to 30 days after the last dose of study drug.

Off-treatment AEs are events with a start date more than 30 days after last dose and not considered treatment emergent. Off-treatment AEs will be summarized separately.

AEs are coded using MedDRA (Medical Dictionary for Regulatory Activities) version 21.1. In MedDRA, each verbatim term is mapped to a preferred term and high level term (HLT), which is then mapped to a system organ class (SOC).

The investigator grades the severity of the AEs as mild, moderate, or severe as defined in the study protocol. The investigator grades association or relatedness to the study medication according to criteria specified in Section 11.4 of the protocol.

As defined in the protocol, a serious adverse event (SAE) is an adverse event (occurring at any dose and regardless of causality) that:

- Results in death;
- Is life-threatening;
- Requires inpatient hospitalization or prolongation of existing hospitalization;
- Results in persistent or significant incapacity or substantial disruption of the ability to conduct normal life functions;
- Is a congenital anomaly or birth defect in an offspring of a patient taking study drug;
- Is an important medical event.

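### The partial-date rules in SAP 5.6.2 conflict in two places with the onset-based definition in SAP 9.1, so a literal program could count late-onset adverse events as treatment-emergent

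*SAP*

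**What the plan says.** SAP 9.1 sets the classification. An event is treatment-emergent if its onset is on or after first dose "and not more than 30 days after the date of the last dose of study drug". A stop date matters only when no onset is recorded. Later events form a separate table: "Off-treatment AEs are events with a start date more than 30 days after last dose and not considered treatment emergent".

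SAP 5.6.2 handles incomplete dates. It opens with a cross-reference, "Treatment-emergent adverse events (TEAEs) are defined in Section 9.1", and then gives two lists:

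- List 1: "Adverse events with incomplete start dates are considered after the date of first dose, and therefore treatment emergent, if" the recorded parts meet one of four conditions. All four compare the date with first dose or accept a missing year. None looks at last dose.
- List 2: "Adverse events with incomplete start dates or end dates are considered on or within 30 days of last dose, if" one of three conditions is met. The first is "Day, month, and year are missing". The other two compare the recorded year, or the year and month, with the date 30 days after last dose.

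SAP 9.1.1 refers back to 5.6.2, but only for the handling of onset dates.

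**The concern.** List 2 covers end dates as well as start dates and does not limit the end-date branch to events whose onset is unknown. A blank end date meets its first condition whatever the onset. An event with a complete onset on, say, day 33 after last dose could then be treated as falling within 30 days.

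List 1 has a separate problem. It declares a partial onset treatment-emergent on the strength of first dose alone, so the 30-day limit in 9.1 is lost for partial dates.

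Safety and tolerability is a primary objective, and the TEAE and off-treatment tables are meant to divide events by when they began. A literal program would divide some of them by whether they had resolved or how fully they were dated. Late events that persist could leave the off-treatment table while resolved, fully dated ones stayed. Exposure to the error is longer after early stopping, so arms that differ in early stopping could be affected differently. The documents give no figures to size that difference.

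**Working it through.** The plan states no figure to reproduce. The check applies both sections to the same events. The calendar dates are illustrative.

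**1. Complete onset, incomplete end date.** Assume first dose on 11 Jan 2021 (Day 1) and last dose on Day 83, since Protocol 7.6.4 puts the last dose the day before the Week 12 visit (Day 84). Last dose = 11 Jan + 82 days = 3 Apr 2021. Limit = 3 Apr + 30 days = 3 May 2021.

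| Onset, days after last dose | Onset date | SAP 9.1 | List 2 applied literally to the end date |
|---|---|---|---|
| 29 | 2 May | TEAE | within 30 days |
| 30 | 3 May | TEAE | within 30 days |
| 31 | 4 May | off-treatment | within 30 days |
| 33 | 6 May | off-treatment | within 30 days |
| 35 | 8 May | off-treatment | within 30 days |
| 38 | 11 May | off-treatment | within 30 days |

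The last column is the same for an end date that is wholly missing, recorded only as 2021 (2021 ≤ 2021), or recorded as May 2021 (year 2021 ≤ 2021, month 5 ≤ 5). The sections agree up to day 30 and conflict beyond it. With end dates removed from List 2, they agree on every row.

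**2. Partial onset after the limit.** Assume first dose on 7 Jan 2021 and last dose on Day 83 = 30 Mar 2021. Limit = 29 Apr; OT Day 35 = 4 May. The onset is recorded as May 2021.

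- List 1: same year as first dose, month 5 ≥ 1, so treatment-emergent.
- List 2: month 5 > 4, so not within 30 days.
- SAP 9.1: the earliest possible onset, 1 May, is after 29 Apr, so off-treatment.

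This contradiction needs no assumption about end dates.

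**3. Length of the exposed period.**

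- Completer: limit = Day 83 + 30 = Day 113. OT Day 35 = Day 83 + 35 = Day 118. Exposed days are 114 to 118, which is 5 days (6 if counted to Week 17, Day 17 × 7 = 119).
- Patient stopping at Week 5, the example in Protocol 8.3.1, with last dose taken as Day 35: limit = Day 65. Follow-up runs to Day 119 because the Week 17 visit is kept. Exposed days = 119 − 65 = 54.

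**4. Would requiring both lists be a safe repair?** Not with List 2 as it stands. Assume first dose on 15 Dec 2020, last dose on Day 83 = 7 Mar 2021, limit 6 Apr 2021, and an onset recorded as December 2020.

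- List 1: same year, month 12 ≥ 12, so treatment-emergent.
- List 2: year 2020 ≤ 2021 passes, but month is tested separately and 12 ≤ 4 fails.

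An event that may have begun on treatment would lose TEAE status. Compared jointly, December 2020 precedes April 2021 and the event is kept. The case is realistic, because both documents estimate first enrolment in December 2020. List 2 also has no condition for a missing year with the month or day present, which List 1 accepts, so those events would drop out too.

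**The case against.** A reader might infer that a continuing event with onset more than 30 days after last dose *is* counted as treatment-emergent. The documents do not support that flat statement. SAP 5.6.2 defers to 9.1 for the definition, and 9.1 classes a known late onset as off-treatment. List 2 never uses the term treatment-emergent; only List 1 does. A programmer who follows 9.1 would classify the event correctly. Nor does the SAP say that the blank end date of an event flagged as continuing is an incomplete date. The related sentence in 9.1, "A TEAE with a missing resolution date or incomplete date that is not identified as continuing is assumed to be continuing", governs the continuing status of an event already classed as a TEAE and does not make an event a TEAE.

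These points stand, and they limit the finding to a risk under literal programming. They do not remove the conflict. The cross-references run both ways, and the closing words of the off-treatment definition can be read as a second condition, so 9.1 does not plainly settle the matter. The reference back from 9.1.1 covers onset dates only, which suggests that end dates do not belong in the list. An end date can bound an unknown onset, but 9.1 already provides for a stop date when no onset is recorded.

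It is also tempting to estimate what share of late events would be relabelled. That needs event durations and onset patterns that neither document supplies. Follow-up differs by event as well. Protocol 11.6 requires drug-related events to be followed to resolution, while "All other AEs will be followed through the final visit indicated in" the schedule table. Protocol 11.2.1.2 follows serious events until they are resolved, chronic or stable. Many blank end dates would therefore be filled later. No share is claimed here.

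**Conclusion.** Both conflicts are present in the SAP text. The end-date conflict matters only if List 2 is programmed literally and its result is carried into the TEAE flag. The partial-onset conflict is explicit in List 1, but arises only when an onset month lies wholly after the 30-day limit.

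The effect is likely to be small. The exposed period is about 5 days for completers and about 54 days for a patient stopping at Week 5, taking last dose as Day 83 and Day 35 respectively. The error runs one way, into the TEAE tables and out of the off-treatment table. It could add a row to the table of TEAEs in more than 5% of patients but could not remove one. All adverse events are listed, SAP section 9 plans no formal safety testing, and no efficacy result depends on these rules. The correction is worthwhile because it is cheap and the present text supports two different derivations.

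**What to change.** In SAP 5.6.2:

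1. Delete *or end dates* from the opening of List 2.
2. State that an event with a complete onset date is classified by SAP 9.1 alone, and that both lists apply only to missing or partial onset dates.
3. In List 1, replace the clause that makes the event treatment-emergent with a condition: it is treatment-emergent if the partial onset could also fall no later than 30 days after last dose.
4. In the same revision, make List 2 compare year and month jointly, and state that an onset with a missing year is kept as treatment-emergent. Step 3 should not be adopted without this step.

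The cost is a few lines of SAP text and a small change to the adverse event derivation, with no new data. If the derivation is already written, confirm which section it follows and rerun the two adverse event tables if it follows 5.6.2 literally.

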**TECHNICAL SUMMARY REPORT (TSR)**

Name of Sponsor/Company: Reata Pharmaceuticals, Inc.	Individual Study Table Referring to Part of the Dossier: Volume:	(For National Authority Use Only):
Name of Finished Product: Bardoxolone methyl capsules	Page:	
Name of Active Ingredient: Bardoxolone methyl		
Title of Study: A phase 2 trial to evaluate safety, tolerability, and efficacy of Bardoxolone Methyl in patients with chronic kidney disease at risk of rapid progression		
Investigators: Study Center(s): 11 Sites used		
Studied period (years): Estimated date first patient enrolled: December 2020 Estimated date last patient completed: July 2021	Phase of development: 2	
Objectives: Primary: 
 
• To assess the change from baseline in estimated glomerular filtration rate (eGFR) at Week 12
 
• To assess the safety and tolerability of bardoxolone methyl
 
 Secondary: 
 
• To characterize the eGFR response at Week 12 across different etiologies of Chronic Kidney Disease
 
 Exploratory: 
 
• To characterize change in eGFR during the off-treatment period
 
		

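### SAP 5.6.2: the 30-day rule for adverse events with a missing day tests year and month separately, so a December 2020 event fails against an early-2021 cut-off and conflicts with the first-dose rule in the same section

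*SAP*

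**What the plan says.** SAP 9.1 requires a dated TEAE to start on or after first dose and "not more than 30 days after the date of the last dose of study drug". SAP 9.1.1 refers partial onset dates to SAP 5.6.2, which has two blocks.

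- **First-dose block.** This decides whether the event is after first dose and, in its own words, therefore treatment emergent. It separates two cases. In one, "Day is missing and the year is after the year of the first date of study drug dosing", and no month test follows. In the other, "the year is equal to the year of the first date of study drug dosing", and only then is the month compared.
- **Last-dose block.** "Adverse events with incomplete start dates or end dates are considered on or within 30 days of last dose, if" one of three bullets is met. The first covers a fully missing date. The second covers a missing day and month and tests the year alone. The third covers a missing day: "Day is missing and the year is equal to or before the year of the date of last dose of study drug plus 30 days", joined by *and* to the condition that the "month is equal to or before the month of the date of last dose of study drug plus 30 days". No bullet covers an earlier year on its own.

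The Technical Summary Report gives the calendar: "Estimated date first patient enrolled: December 2020". Dosing lasts 12 weeks, so treatment that runs across the year end is expected for the first patients.

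**The concern.** Dates should be compared in order: year first, and month only when the years tie. The last-dose bullet instead requires both parts to be at or below the cut-off separately. An event late in one year therefore fails against a cut-off early in the next, although it is months before it. The first-dose block of SAP 5.6.2 and the concomitant-medication rule in SAP 5.6.1.3 both handle this correctly, so the last-dose bullet looks like a drafting slip and not a deliberate choice.

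What is at stake is how a few on-treatment events are classified in the TEAE tables. Safety and tolerability is one of the trial's two primary objectives, and those tables are its main AE summary.

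**Working it through.** The plan states no figure here, so there is none to reproduce. The check applies the rule as written to dates that the documents make plausible.

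**Inputs**
- First dose in December 2020 (estimated first enrolment; Protocol synopsis and SAP Technical Summary Report).
- Last dose on the day before the Week 12 visit (Protocol 7.6.3 and 7.6.4). With that visit on Day 84, last dose is on Day 83 = first dose + 82 days.
- Cut-off C = last dose + 30 days (SAP 5.6.2 and 9.1).
- Event: December 2020, day unknown.

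**Rules compared**
- As written: year(event) ≤ year(C) AND month(event) ≤ month(C).
- Chronological: year(event) < year(C), OR years equal and month(event) ≤ month(C).

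| First dose | Last dose (Day 83) | Cut-off C | Year test | Month test | As written | Chronological |
|---|---|---|---|---|---|---|
| 1 Dec 2020 | 21 Feb 2021 | 23 Mar 2021 | 2020 ≤ 2021, true | 12 ≤ 3, false | fails | passes |
| 15 Dec 2020 | 7 Mar 2021 | 6 Apr 2021 | 2020 ≤ 2021, true | 12 ≤ 4, false | fails | passes |
| 31 Dec 2020 | 23 Mar 2021 | 22 Apr 2021 | 2020 ≤ 2021, true | 12 ≤ 4, false | fails | passes |

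**All December starts.** Taking each first dose from 1 to 31 December 2020 with each last dose from Day 1 to Day 83 gives 31 × 83 = 2573 date pairs.
- Last dose in 2021: 2077 of 2077 pairs wrongly fail.
- Last dose still in December 2020: 495 of 496 wrongly fail, because adding 30 days moves C into January 2021. The exception is a last dose on 1 December, where C is 31 December 2020.
- Under the chronological rule, no pair fails.

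**When the written rule would pass.** With a last dose in 2021, C must fall in December 2021, so last dose must lie between 1 November and 1 December 2021. That is after the estimated completion in July 2021.

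**Where the error stops.** If event and cut-off both fall in 2021, the written and chronological rules agree.

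**Consistency within SAP 5.6.2**
- First-dose block, same event: year equal and month equal, so it is met and the event is called treatment emergent.
- Year-only bullet: an AE dated only 2020 gives 2020 ≤ 2021 and passes. An AE dated December 2020, which is better dated, fails.

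**The case against.** The strongest reply is that the SAP never says a failing event is outside the treatment-emergent window. The last-dose block lists when events count as within 30 days and says nothing about the rest. SAP 9.1 defines off-treatment AEs as starting more than 30 days after last dose and not being treatment emergent. A December 2020 event in a patient dosed that month cannot have started that late, whatever the missing day. The first-dose block calls it treatment emergent outright, and it stays in the listing of all AEs. This stands. A reader might infer that such events are definitely removed from the TEAE tables or moved to the off-treatment summary. The text does not support that; it gives conflicting answers.

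A reader might also infer that early fluid-overload events could disappear, since Protocol 5.1.2.1 places that risk in the first four weeks. The documents do not support this either. AE onset dates are recorded (Protocol 11.6), and AEs are reviewed at Day 3, Week 1, Day 10 and Weeks 2, 3 and 4 (Protocol Table 4). Suspected fluid retention leads to medical evaluation within 1 to 2 days (Protocol 9.1.1), and serious events are reported within 24 hours of site awareness (Protocol 11.7). These are the events least likely to lack a day of onset.

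Finally, *month* could be read as calendar month with its year, and the event would then pass. That reading makes the separate year condition redundant and does not match the sibling rules. A rule that depends on it still needs clarifying.

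**Conclusion.** The wording defect is certain on the literal text. The day-missing bullet gives the wrong answer for a December 2020 event whenever last dose plus 30 days falls in early 2021. It also contradicts both the first-dose block and the year-only bullet. Two programmers could classify the same event differently, and one who applies the 30-day bullet literally could leave it out of the TEAE tables. The documents do not establish that any event would in fact be excluded.

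The effect is probably very small and may be nil. It requires a patient actually dosed in December 2020, an AE starting that month, and a missing day, in a trial of about 70 patients. The December start is an estimate, and the documents do not say how many patients began then or how many AEs have partial dates. Efficacy analyses do not use this rule. This is a minor correction.

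**What to change.** Replace the third bullet of the last-dose block in SAP 5.6.2 with two:

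- the day is missing and the year is before the year of last dose plus 30 days; or
- the day is missing, the year equals that year, and the month is the same as or before the month of last dose plus 30 days.

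This follows the structure of the first-dose block and of SAP 5.6.1.3. It would also help to state that a partial-date event counts as a TEAE only when both blocks are met, so that the first block is not read as sufficient alone.

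The cost is one SAP sentence and one line of code, with no effect on any other analysis. If the AE programs already exist, check how the bullet was coded and list any December 2020 AEs with a missing day. An empty list shows that the slip had no consequence.

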## 6. STUDY POPULATION

### 6.1. Subjects Disposition

A disposition summary includes the number and percentage of patients in all analysis populations in the following categories:

#### Disposition

- ITT population
- Safety population
- Completed treatment through Week 12
  - Week 12 visit in analysis window
  - Week 12 visit out of analysis window
  - Week 12 visit missing
- Discontinued treatment prior to Week 12
  - Reason for discontinuing treatment
- Completed study through Week 17
  - Completed On-treatment and Off-treatment visits
  - Discontinued treatment early but completed in-person study visits
  - Discontinued treatment early but completed by phone
- Terminated from the study before Week 12
  - Reason for study termination
- Terminated from the study before Week 17
  - Reason for study termination
- Completed through Week 17
- Completed treatment through Week 12 and off-treatment assessments through Week 17
- Summaries by study visit
  - On treatment
  - Off treatment
  - In study
  - Stopped study

